2.2 Primary Hypotheses: Route of administration

The primary efficacy hypotheses to be tested in the continuous infusion vs. intermittent bolus comparison are:

- That continuous IV infusion of furosemide causes less renal dysfunction than twice daily IV bolus administration, as measured by change in creatinine from baseline to 72 hours
- That continuous IV infusion of furosemide is more efficacious at relieving acute symptoms compared to twice daily bolus administration, as measured by the area under the curve of serial visual analog assessments for global well being over 72 hours

These hypotheses will be evaluated in the context of a randomized controlled clinical trial using a 2 x 2 factorial design. Each factor (main effect) in the design will be tested at the α =0.025 level.

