14.2 Analysis of Primary Endpoints

The primary analysis will be made on an intention-to-treat basis, with patients allocated to the treatment to which randomized. General linear models will be used to examine the effect of each of the main effects on the two co-primary outcomes. The dependent variables in the regression model will be the change in creatinine value from baseline to 72 hours and the AUC for the PGA VAS from baseline through 72 hours. Independent variables in the model will include the main effects of furosemide dose and mode of administration, and the baseline creatinine level. An interaction term will be included if the p-value for that parameter estimate is less than 0.025. For each co-primary outcome, the two main effects will be that the treatment (either dose or mode of administration) has no effect on either of the co-primary outcomes.

We anticipate that some patients may die before all scheduled post-baseline creatinine values can be taken, and that these losses will introduce bias into the main effects comparisons. For the primary analyses, the values imputed will be 0 for the PGA VAS after the time of death and the highest post-baseline creatinine measurement. Sensitivity analyses, including analysis of only complete cases and imputing the worst creatinine value for deaths, will be employed to assess the degree to which these missing values impact the results.

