14.3 Sample Size

For purposes of power calculations, we have applied a Bonferroni adjustment to the alpha level (0.05/2 = 0.025) to allow for two co-primary endpoints. We assume that the effect of both dose and administration mode will be additive (i.e. no interaction). In our sample size calculations shown below we assess the sensitivity of the power to subadditivity of the main effects. Due to the short-term nature of the study, missing data due to loss-to-followup are expected to be rare. In addition, because this study design is testing initial treatment strategies, we do not anticipate problems with adherence to the protocol guidelines.

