14.3.1 Change in Creatinine at 72 hours

The standard deviation observed for the change in creatinine from baseline to discharge in the ESCAPE trial (unpublished data) was 0.47 mg/dL. Similarly, in the control arm of the UNLOAD study (unpublished data), the standard deviation of the change in creatinine from baseline to discharge was 0.5 mg/dL. With 300 patients, we will have approximately 88% power to detect a difference in mean creatinine of 0.20 mg/dL for each main comparison, assuming a standard deviation of 0.5 mg/dL. Assuming a smaller standard deviation of 0.4 mg/dL, we would have approximately 98% power to detect a difference of 0.2 mg/dL. The effect of various standard deviations on the power to detect given mean differences in peak creatinine (mg/dL) at the 2.5% significance level is given in Figure 5.

Figure 5. Power with 150 patients per group to detect various mean differences in creatinine (mg/dL) assuming normal distribution with various standard deviations at the two-sided 2.5% significance level

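### The primary model depends on an interaction pre-test, and nothing fixes the marginal main effect as the tested contrast once the interaction term enters

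*Protocol*

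**What the plan says.** Protocol section 14.2 sets the aim of the primary analysis: "General linear models will be used to examine the effect of each of the main effects on the two co-primary outcomes". The base model is additive: "Independent variables in the model will include the main effects of furosemide dose and mode of administration, and the baseline creatinine level". A conditional step follows: "An interaction term will be included if the p-value for that parameter estimate is less than 0.025". The section does not state how the factors are coded, or which contrast represents the main effect of dose or route once the interaction is in the model.

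The rest of the protocol works with main effects. Section 2.2 says: "Each factor (main effect) in the design will be tested at the α =0.025 level". Section 14.3 assumes that the two effects are additive and explains the level: "we have applied a Bonferroni adjustment to the alpha level (0.05/2 = 0.025) to allow for two co-primary endpoints". Section 14.3.1 gives about 88% power for a creatinine difference of 0.20 mg/dL in each main comparison (SD 0.5, 150 per group, two-sided 2.5%). Table 1 in section 14.3.2 gives main-effect power when additivity fails: 30% under subadditivity (scenario 2) and 99% under superadditivity (scenario 3).

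**The concern.** In a 2x2 factorial trial the main effect of dose is its effect averaged over the two routes, estimated from 150 v 150 patients. In a model with an interaction term, the coefficient labelled dose has that meaning only under effect (sum-to-zero) coding, or if a marginal contrast is requested. Under reference (0/1) coding it is the effect of dose within the reference route alone, estimated from 75 v 75. A rule that adds the term on the strength of the observed p-value, without fixing the contrast, lets the quantity being tested change with the data.

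Three things are at stake: the 2.5% level of each primary test, the planned power, and a result that could depend on which route or dose is declared the reference. The rule also works outcome by outcome, so creatinine and the global assessment AUC could be reported from different models that answer different questions.

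**Working it through.** **Inputs.** 75 patients per cell and 150 per level of each factor (section 5); SD 0.5 mg/dL and difference 0.20 mg/dL (section 14.3.1); two-sided 0.025, critical value 2.241; interaction threshold 0.025 (section 14.2); cell means from Table 1. Balanced cells and normal theory are assumed.

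**Standard errors.**
- Marginal main effect: 0.5 × √(2/150) = 0.0577
- Simple effect within one level: 0.5 × √(2/75) = 0.0816
- Interaction contrast: 0.5 × √(4/75) = 0.1155

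**The plan's own figures.** Power for 0.20 at 150 v 150 is Φ(0.20/0.0577 − 2.241) = 88.9% (88.6% with the noncentral t), against 88% stated. With SD 0.4 it is 98.2%, against 98%. For the AUC (600 points, SD 1500) it is 88.9%, against 88%. These agree.

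**Which effect Table 1 targets.** In scenario 2 the dose effect is 0.3 − 0.1 = 0.2 under infusion and 0.3 − 0.3 = 0 under bolus, an average of 0.1. Marginal power is Φ(0.1/0.0577 − 2.241) = 30.5%, which matches the stated 30%. The simple effects would give 58% or 2.5%. So even with an interaction present, the design calculation targets the marginal effect.

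**The two-stage rule.** In a balanced design the main-effect and interaction statistics are independent. The simple-effect statistic is (Z_main ± Z_int)/√2, with the sign set by the reference level. Let p be the probability that the term enters. Then

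P(reject) = (1 − p) × P(marginal test rejects) + p × P(simple-effect test rejects, given that the term entered).

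If the marginal contrast is tested throughout, independence leaves the rejection rate at its nominal value. A simulation with a baseline covariate (100,000 trials) gave 2.52% under the global null.

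Under reference coding, for dose:

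| Case | p | Marginal test | Given that the term entered | Two-stage result |
|---|---|---|---|---|
| Global null | 2.5% | 2.5% | 28.8% | 3.16% |
| Scenario 1 (additive, 0.2) | 2.5% | 88.9% | 51% | 88.0% |
| Scenario 2, infusion as reference | 30.5% | 30.5% | 90.3% | 48.8% |
| Scenario 2, bolus as reference | 30.5% | 30.5% | 4.0% | 22.4% |
| Scenario 3, infusion as reference | 30.5% | 99.8% | 22.5% | 76.2% |
| Scenario 3, bolus as reference | 30.5% | 99.8% | >99.9% | 99.9% |

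For example, global null: 0.975 × 0.025 + 0.025 × 0.288 = 0.0316. Scenario 2 with infusion as reference: 0.695 × 0.305 + 0.305 × 0.903 = 0.488. The simulation agrees: 3.21% under the null, and 47.4% and 76.6% for scenarios 2 and 3 with infusion as reference. Route gives the same values, because Table 1's cells are symmetric in the two factors.

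**Power of the pre-test.** The interaction contrast in scenarios 2 and 3 is 0.2 mg/dL in absolute size: Φ(0.2/0.1155 − 2.241) = 30.5%. The term would be left out about 70% of the time. Table 1 states 57%. A value near that (58%) results only with the simple-effect standard error. That discrepancy needs its own correction.

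**Different models for the two outcomes.** With no interaction on either outcome, and treating the two pre-tests as independent (an assumption), exactly one model would gain the term with probability 2 × 0.025 × 0.975 = 4.9%.

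**The case against.** The strongest reply is that the protocol says main effect throughout and Table 1 computes it as the marginal effect even where additivity fails, so the natural reading is that the marginal contrast is tested whichever model is fitted. Coding and contrast statements also belong in a statistical analysis plan, which is not shown. On that reading each test keeps 2.5% and the power stands. A triggered interaction term can also be a useful prompt to report results by cell.

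Much of this stands, and it rules out some stronger readings. A reader might infer that the pre-test inflates the type I error as such. It does not: the inflation needs a simple effect to be tested, and the protocol nowhere says that one will be. The 28.8% false-positive rate given inclusion concerns an event with 2.5% probability under the null and means little apart from the overall 3.16%. A reader might also infer that power falls to 58% whenever the term enters. That is the power of a free-standing 75 v 75 comparison; given inclusion under additivity it is about 51%, and overall power falls by only about one percentage point. Nor is the reported effect necessarily exaggerated: at the design effect, the simple effect given inclusion is smaller than the marginal one about half the time.

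What the reply does not remove is the rule itself. It is protocol text, and an analysis plan that named the contrast would still inherit a model chosen by the data. Under the benign reading the sentence adds essentially nothing to the main-effect tests. Cell results can be promised without it.

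**Conclusion.** The point holds in a limited form. Section 14.2 makes the primary model conditional on an observed p-value and does not secure the marginal main effect that sections 2.2 and 14.3 and Table 1 are built on. Whether harm follows depends on a contrast that the protocol does not state. With the marginal contrast there is none. With a reference-coded coefficient, the cost is small under the global null (2.5% to about 3.2% per test) and under additivity (about 89% to 88%). It is substantial if an interaction of Table 1's size exists: the chance of a significant dose result differs by about 26 percentage points in scenario 2 and 24 in scenario 3 according to the reference level alone. With a pre-test power of about 30% for 0.2 mg/dL, the rule is also a poor safeguard against non-additivity.

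These figures assume 75 patients per cell, SD 0.5 mg/dL, normal errors and Table 1's hypothetical means. Slight imbalance from blocking within site would make the independence argument approximate. The correction should be made because it is nearly free and removes the ambiguity.

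**What to change.** Delete the conditional-inclusion sentence from section 14.2. State instead that, for both co-primary outcomes and whatever the interaction p-value, the primary test of each factor is its marginal main effect at two-sided 0.025, from the additive model or the equivalent marginal contrast, with one of the two named in advance. Add that the dose-by-route interaction will be reported with its confidence interval, together with the four cell means, as supportive results.

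This keeps each test at 2.5% under the global null and preserves the stated 88% power. It costs a sentence or two of protocol text, needs no further data or patients, and loses no information about the interaction.

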5. BASIC STUDY DESIGN

This study will be a randomized, controlled, multi-center clinical trial of patients with signs and symptoms consistent with AHF within 24 hours of hospital admission. A total of 300 patients will be enrolled in the trial.

Patients will be randomized to one of 4 treatment regimens (75 patients / treatment regime) defined by a 2x2 factorial treatment design:

1) "High intensification" strategy for IV furosemide (defined as 2.5 x stable PO home dose) vs. "low intensification" dose IV furosemide (defined as 1 x stable PO home dose). This treatment will be double-blinded.

2) Continuous furosemide IV infusion vs. IV furosemide given as IV bolus Q12 hours. This treatment will be double-blinded.

The study treatment regimen will be administered from randomization through 48 hours, at which point the investigator may modify the IV loop diuretic strategy based on clinical assessment of the patient and their response to therapy. Permitted modifications will be:

- 1. Continue current strategy without change
- 2. Increase dose by 50% (while remaining blinded to both dose and route of administration assignment)
- 3. Switch to oral furosemide (dose at the investigator's discretion) in preparation for discharge.

Blinding of initial treatment assignment will be maintained regardless of which of the options are selected.

After 72 hours, all diuretic treatment will be open label at the treating physician's discretion.

The primary assessment for both efficacy and safety will occur at 72 hours after randomization.

The primary endpoint for efficacy will be patient reported global well being by visual analog scale (VAS) quantified as the area under the curve (AUC) over 72 hours.

The primary safety endpoint will be change in serum creatinine from baseline to 72 hours.

Anticipated need for at least 48 hours of IV diuretic therapy will be an inclusion criterion for the study. However, if patients are deemed to have achieved adequate diuresis before 48 hours, they may be switched to oral dosing of diuretics (open label) at the investigators discretion. If patients are discharged prior to 72 hour assessment, the last VAS

DOSE protocol version 18.1; February 4, 2008

assessment and last serum creatinine will be carried forward to 72 hours for the purposes of assessing the primary endpoints.

If patients die prior to 72 hour assessment, the last serum creatinine will be carried forward and the last VAS will be imputed as 0.

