10. FOLLOW UP EVALUATIONS

Follow-up evaluations are expected to occur within +/- 2 hours of the nominal time points.

10.1 6 and 12 hours

- PGA assessment by VAS
- Dyspnea assessment by VAS

10.2 24, 48, 72, and 96 hours

On study days 1-4, all study subjects will undergo the following assessments daily:

- Directed history and physical examination, focused on signs and symptoms of congestion
- Vital signs (including O₂ saturation and weight)
- Creatinine, BUN, and electrolytes (local laboratory)
- PGA assessment by VAS at 24, 48, 72, and 96 hours
- Dyspnea assessment by VAS at 24, 48, 72, and 96 hours
- Fluid balance over preceding 24 hours (net intake net output)
- Blood sample for biomarkers core laboratory (72 hours only)
- Changes in cardiovascular medications
- Assessment for adverse events

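### The section 14.2 rule for deaths leaves baseline out of the maximum, so a death with every later creatinine below baseline scores as a renal improvement, and section 5 sets a different rule for the same patients (minor)

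*Protocol*

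**What the plan says.** Section 5 defines the endpoint: "The primary safety endpoint will be change in serum creatinine from baseline to 72 hours". Three statements in the Protocol bear on how a death before 72 hours is scored.

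- **Section 14.2, primary analysis:** the imputed values are "0 for the PGA VAS after the time of death and the highest post-baseline creatinine measurement". The same section promises intention to treat: "The primary analysis will be made on an intention-to-treat basis".
- **Section 5, deaths:** "If patients die prior to 72 hour assessment, the last serum creatinine will be carried forward and the last VAS will be imputed as 0". This is not limited to post-baseline values.
- **Section 14.2, sensitivity:** "Sensitivity analyses, including analysis of only complete cases and imputing the worst creatinine value for deaths, will be employed". It does not say whether the worst value is the patient's own or one taken from the whole trial.

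On timing, section 10.1 and Appendix A show only VAS assessments at 6 and 12 hours. Creatinine starts with the daily visits of section 10.2: "On study days 1-4, all study subjects will undergo the following assessments daily". The first scheduled post-baseline creatinine is therefore at 24 hours.

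**The concern.** Section 14.2 expects deaths to bias the comparison and sets a rule to deal with that. The PGA half gives a death the bottom of the scale. The creatinine half takes a maximum, which suggests the same intention, but the maximum runs over post-baseline values only. Nothing stops it from falling below baseline, and then a death is recorded as better renal function. The rule also returns nothing for a patient without a post-baseline draw.

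At stake is the meaning of a co-primary safety endpoint in a trial that section 4.1 motivates partly by a dose-related mortality signal. Section 5 adds a second rule for the same patients, so the Protocol does not settle which value enters the primary model.

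**Working it through.** **1. The plan's own figure.** Inputs from section 14.3.1: 150 per group, difference 0.20 mg/dL, SD 0.5, two-sided alpha 0.025. The standard error is 0.5 × √(2/150) = 0.0577. Power is Φ(0.20/0.0577 − 2.241) = 0.889 (0.886 with the noncentral t), against the stated 88%. The design figure reproduces and is not in dispute.

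**2. The rules applied to example patients** (illustrative values; baseline 2.0 mg/dL, death before 72 h; entries are the imputed change).

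| Post-baseline values | 14.2: highest post-baseline | Section 5: last value | Highest, baseline included |
|---|---|---|---|
| 1.7 | -0.3 | -0.3 | 0.0 |
| 1.8, 1.6 | -0.2 | -0.4 | 0.0 |
| 2.4, 1.8 | +0.4 | -0.2 | +0.4 |
| none | undefined | 0.0 | 0.0 |

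The improvement arises under 14.2 only when every post-baseline value is below baseline. In the third row, sections 14.2 and 5 give opposite signs.

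**3. How often a post-baseline maximum is negative.** Planning means m = 0.1, 0.3 and 0.5 come from the additive scenario of Table 1, read as changes. The SD is 0.5. Assumptions: normal changes, the same mean at each draw, and correlation 0.7 between two draws.

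- One draw: Φ(−m/0.5) = 0.42, 0.27, 0.16.
- Two draws, both negative (bivariate normal): 0.30, 0.17, 0.08.

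**4. How many deaths.** The Protocol gives no 72-hour figure. Section 3 cites 20-30% six-month mortality. With a constant hazard, 300 × [1 − (1 − q)^(3/182.5)] = 1.1 for q = 0.20 and 1.8 for q = 0.30. Affected deaths, if each has at least one draw: 1.1 × 0.08 ≈ 0.1 up to 1.8 × 0.42 ≈ 0.7. If 2% died by 72 h (an assumption), there would be 6 deaths, of which 6 × 0.08 ≈ 0.5 to 6 × 0.42 ≈ 2.5 are affected.

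**5. Size per affected death.** In the same model the mean of a negative score runs from about -0.22 (two draws, m = 0.5) to -0.36 (one draw, m = 0.1). Scoring it 0 instead moves a group mean by 0.22/150 ≈ 0.0015 to 0.36/150 = 0.0024 mg/dL, which is 0.7% to 1.2% of 0.20. With 2.5 affected deaths all in one group, the shift is 2.5 × 0.0024 = 0.006, or 3% of 0.20.

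**6. Effect on power, as a deliberately adverse case.** Suppose 1 to 5 excess deaths in one group are each scored -0.2 instead of 0, and the whole shift masks a true 0.20 difference. The shift is 0.2/150 = 0.0013 to 1.0/150 = 0.0067, and power falls from 0.889 to between 0.885 and 0.866.

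**7. Deaths against survivors.** A patient assessed at 72 h is scored on one value, with mean m. A death after one draw also averages m. A death after two draws averages m + 0.5 × √(0.3/π) = m + 0.155. On average the rule is neutral or scores deaths worse.

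**The case against.** The strongest counter-case has four parts.

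- **Section 5 covers the early death.** It would return baseline, a change of 0, and 14.2 does not exclude an unscheduled draw before 24 hours. This stands: a reader might infer that early deaths must drop out of the model, but the Protocol as a whole does not say so. The gap belongs to 14.2 alone. Because section 5 conflicts with 14.2 elsewhere, though, it is not a dependable rescue.
- **The sensitivity analyses already address it.** This holds in part. If the worst value means something harsher than the patient's own maximum, that analysis does the job, but the term is undefined. If it means the patient's own highest post-baseline value, it repeats the primary rule. The complete-case analysis drops the deaths.
- **There is no systematic bias in favour of deaths.** A reader might infer that the arm with more deaths, or earlier ones, will look better on renal safety. Step 7 does not support that, and negative changes occur among survivors too. Later deaths do score about 0.155 higher than earlier ones in this model, but that does not place earlier deaths below survivors.
- **A falling creatinine is not enough.** A reader might also infer that any death with creatinine on the way down counts as improvement. The sequence 2.0, 2.4, 1.8 scores +0.4 under 14.2, so that reading is too broad.

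What remains is a defect of definition that the Protocol fixes in its own text, so it cannot simply be left to an analysis plan.

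**Conclusion.** The point holds in a limited form. Under section 14.2 a death whose post-baseline creatinines are all below baseline is recorded as a renal improvement. A death with no post-baseline draw has no value there. Section 5 prescribes a different imputation that can reverse the sign.

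The expected effect is very small: about 0.1 to 0.7 affected patients in the whole trial, and roughly 1% of the design difference for each. These figures rest on an even spread of the cited six-month mortality, normal changes with the planning means and SD, and an assumed correlation of 0.7. A higher early death rate raises the count but leaves the shift small, as the 2% case shows. Severity is minor. The reason to act is that the rule should be unambiguous and should not credit a death with improved renal function.

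**What to change.** Make three edits to the text, none of which needs new data.

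1. In section 14.2, impute for deaths *the highest creatinine recorded from randomization to death, baseline included*.
2. In section 5, replace the last-value rule for deaths with the same wording, so that one rule governs the primary analysis. Changing 14.2 alone would leave the conflict in place.
3. In the section 14.2 sensitivity analysis, define the worst creatinine as a value harsher than the patient's own maximum and say where it comes from.

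Every death with a baseline value then has a score, and none can be below 0. The cost is that deaths with all values below baseline score 0 instead of a negative change, which makes that group's mean slightly less favourable. Deaths with no post-baseline draw also score 0. That is neutral and not a penalty, and it lies below the planning means of 0.1 to 0.5, so it is slightly more favourable to that group than leaving those patients out. The harsher sensitivity analysis in edit 3 is what tests that choice.
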